4.1.2 Practitioner Outcomes

- **Target Population:** Nurses and clinical practitioners involved in managing musculoskeletal symptoms in breast cancer patients.
- **Assessment Tool:** The “Survey on Nurses' Knowledge, Attitude, and Practice (KAP) Regarding Musculoskeletal Symptom Management in Breast Cancer Patients Undergoing Endocrine Therapy in a Multicultural Context.” Pre- and post-intervention comparisons will be conducted to assess knowledge, attitudes, and practice skills.

- **Expected Outcomes:** Nursing staff will demonstrate significant improvements in knowledge, beliefs, and practical skills in managing musculoskeletal symptoms, promoting evidence-based nursing practices.

4.1.3 System Outcomes

- **Expected Outcomes:** This study aims to optimize and standardize the management processes for musculoskeletal symptoms related to endocrine therapy in breast cancer patients. By developing a standardized management protocol, we expect to improve the quality and efficiency of clinical nursing, supporting the advancement and optimization of clinical nursing systems.

4.2 Intervention Participants (Who)

4.2.1 Target Population

Patients undergoing endocrine therapy after early-stage breast cancer surgery.

- **Inclusion Criteria:**
 - Pathologically confirmed hormone receptor-positive (HR+) breast cancer patients.
 - Aged 18 years or older.
 - Currently receiving aromatase inhibitor therapy (e.g., anastrozole, letrozole, exemestane) for at least 6 months.
 - Reports musculoskeletal symptoms induced by endocrine therapy before enrollment.
 - Capable of understanding the study and willing to sign informed consent.
- **Exclusion Criteria:**
 - Patients with a history of fracture or surgery within the past 6 months.
 - Patients diagnosed with arthritis (e.g., rheumatoid arthritis).
 - Patients diagnosed with osteoporosis according to WHO criteria (T-score \leq -2.5).
 - Patients with recurrent or metastatic breast cancer.
 - Patients with other primary malignancies.
 - Patients with severe heart, brain, liver, or kidney dysfunction, or infectious diseases.

- Patients with severe mental, cognitive, or behavioral disorders that hinder understanding or participation in the study.

4.2.2 Intervention Team

- **Nursing Manager (1):** Responsible for human resource management, task allocation, and nursing supervision within the intervention team.
- **Project Coordinator (1):** Manages project progress, coordinates communication and cooperation among departments, and ensures adherence to the study plan.
- **Recruitment, Intervention, and Follow-Up Staff (2-3):** Responsible for patient recruitment, intervention implementation, and follow-up management, including patient enrollment, intervention execution, and periodic follow-up to ensure data collection and sustained patient participation.

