3.1 Sample Size

The primary measurement tool for this study is the Western Ontario and McMaster Universities Osteoarthritis Index (WOMAC), used to assess aromatase inhibitor-related musculoskeletal symptoms in breast cancer patients. The sample size estimation is based on effect size and standard deviation data from previous studies, with a significance level of $\alpha=0.05$ and a statistical power of 80%. The calculated effect size is 0.78. Based on these parameters, each group requires 26 patients, with an additional 20% to account for potential attrition, resulting in a total of 33 patients per group.

Each research site will thus recruit 33 patients for both the intervention and control groups.

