3.3 Allocation Concealment

To prevent allocation bias, this study uses an allocation concealment technique. The randomization sequence will be managed by an independent third party, ensuring that the clinical research team is unaware of patient group assignments prior to allocation. In practice, the randomization results will be sealed in opaque envelopes, which will be opened by independent personnel after each patient's enrollment to determine group allocation. This blinding method minimizes potential bias and interference during study implementation.

4. Intervention Plan

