According to the World Health Organization (WHO) bone density diagnostic criteria^[9], the T-score ranges are as follows:

- Normal: T-score ≥ -1
- Low Bone Mass (Osteopenia): T-score between -1 and -2.5
- Osteoporosis: T-score ≤ -2.5

【Grip Strength】

Grip strength will be measured at months 0, 1, 3, and 6 by the exercise team. This measurement primarily evaluates the forearm flexor and hand muscles, representing forearm muscle strength. An electronic handgrip dynamometer will be used. The subject stands with arms relaxed and hanging down, palms facing the thighs, and the dominant arm (non-surgical side) abducted to a 30-degree angle. The participant grips the dynamometer without swinging the arm, squatting, or allowing the dynamometer to touch the body. Each participant will undergo three assessments, with the highest value used for analysis. A 60-second rest interval is provided between each measurement. Reference standards for grip strength are based on normal values from a large-scale national health survey in China.

Normative values for absolute and relative hand grip strength, stratified by sex and age.

	Male (n = 16 263)								Female (23 392)							
	n	Centiles					Mean	SD	n	Centiles					Mean	SD
		5th	25th	50th	75th	95th				5th	25th	50th	75th	95th		
HGS (kg)																
Age groups																
8-	170	6	8	10	12	16	10.08	2.94	217	4	6	8	10	13	8.14	2.65
10-	211	8	10	13	15	19	13.03	3.64	236	6	9	11.5	14	18	11.65	3.68
12-	237	10	15	18	23	33	19.5	6.74	201	10	14	17	20	24	16.94	4.53
14-	180	16.5	24	28	33.5	40.5	28.46	7.26	185	13	16	20	22	27	19.75	4.35
16-	183	26	31	36	40	48	35.77	6.71	314	15	18	21	24	29	21.52	4.23
18-	212	27	33.5	38	42	51	38.12	7.57	293	16	20	23	26	31	23.19	4.98
20-	1922	30	37	42	48	55	42.46	7.59	2998	16	21	24	28	33	24.44	5.02
30-	2874	30	37	42	47	55	42.12	7.56	4631	18	22	26	29	34	25.55	5.16
40-	4085	28	36	40	46	53	40.75	7.56	6400	16	22	25	28	34	24.96	5.25
50-	3362	26	32	37	42	51	37.61	7.66	4491	14	19	22	26	30	22.34	4.92
60-	2034	20	28	32.15	38	46	32.91	7.32	2521	12	17	20	23	28	19.95	4.76
70-80	731	16	22	27	32	40	27.07	7.15	820	10	14	17	20	25	17.31	4.75
Overall	16 201	20	32	38	44	52	37.72	9.67	23 307	14	20	23	27	32	23.23	5.80

Figure 2: Reference Standard for Grip Strength

【Audit Record Table】

Table 7: Audit Record Table

Serial Number	Audit criteria	Compliance Status	Remarks

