9.1 Baseline Survey Form - Musculoskeletal Symptom Form

Dear Patients,

In order to better understand your condition during endocrine therapy and to help us provide you with appropriate treatment and care, we have designed the following questionnaire to assess your physical and psychological status. The information you provide will serve as a valuable reference for clinical medical and nursing work. We kindly ask that you fill out the questionnaire thoroughly, reflecting your true situation. Some questions may be completed by medical personnel on your behalf.

We sincerely thank you for your participation, support, and cooperation!

- *There are no right or wrong answers. Please respond based on how you usually feel and act.*
- *Please fill out the form based on your actual situation.*
- *For items with a ☐, please place a "✓" in the appropriate box.*

☐ **Outpatient** ☐ **Inpatient**

Outpatient/Inpatient Number: _____

Enrollment/Follow-up Date: _____

Investigator's Signature: _____

I. General Information

1. Gender:

☐ Male ☐ Female

2. Age: _____ years

3. Height: _____ cm Weight: _____ kg

4. Religious Belief:

☐ None ☐ Buddhism ☐ Christianity ☐ Islam ☐ Other

5. Do you regularly participate in religious activities or prayer?

☐ Never ☐ Occasionally ☐ Sometimes ☐ Frequently

6. How much does your religious belief influence your lifestyle?

☐ No influence ☐ Slight influence ☐ Some influence ☐ Significant influence

7. Educational Level:

☐ Primary school or below
☐ Middle school
☐ Technical school/High school
☐ College/University
☐ Graduate degree or higher

8. Employment Status:

☐ Unemployed ☐ Part-time job ☐ Full-time job ☐ Retired ☐ Homemaker

9. Marital Status:

☐ Single ☐ Married ☐ Divorced ☐ Widowed

10. Living Situation:

☐ Stable ☐ Unstable ☐ Homeless

11. Medical Expenses:

☐ Fully self-paid
☐ Mostly self-paid
☐ Partially self-paid
☐ No self-payment

12. Economic Pressure:

☐ None ☐ Slight ☐ Some ☐ Significant

13. Understanding of your disease:

☐ Not at all ☐ Slightly ☐ Somewhat ☐ Very well

II. Medical History

1. Diagnosis Date: _____ Year _____ Month

2. Surgical Approach: _____

3. Pathological Type: _____ (e.g., ductal carcinoma, lobular carcinoma, ductal carcinoma in situ, lobular carcinoma in situ, inflammatory breast cancer, mucinous carcinoma, medullary carcinoma) (may consult healthcare professionals for completion)

4. Comprehensive Treatment Plan:

☐ Chemotherapy: _____ ☐ Radiotherapy: _____

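### Delivery, follow-up data collection and symptom assessment sit in one intervention team, staff completion of WOMAC items is not excluded, and section 3.3 calls envelope concealment blinding

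*Protocol*

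**What the plan says.** **Who does what.** Section 4.2.2 describes a single staff category of two or three people as "Responsible for patient recruitment, intervention implementation, and follow-up management", and the same entry ties periodic follow-up to data collection. Section 4.4.2 lists regular assessment of musculoskeletal symptoms among the measures that the intervention team carries out at each centre, with treatment plans adjusted on the results.

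**What is measured.** Section 3.1 makes WOMAC the primary tool. The form in section 9.1 contains the knee and hip items and the hand items. It has a date field covering both enrolment and follow-up, and its introduction says: "Some questions may be completed by medical personnel on your behalf". In section 6, under Grip Strength: "Grip strength will be measured at months 0, 1, 3, and 6 by the exercise team". That team is not among the roles in section 4.2.2.

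**What is said about blinding.** Section 3.3 has opaque sealed envelopes, a sequence held by a third party, and independent personnel who open the envelope after enrolment. It ends: "This blinding method minimizes potential bias and interference during study implementation". Section 3.2 gives the control group standard care. The protocol does not blind or separate outcome assessors anywhere.

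**The concern.** WOMAC scores are the patient's own ratings of pain, stiffness and difficulty. The intervention consists of nurse training, an app or written and audio materials, and telephone follow-up, set against standard care, so patients and providers know the arm. If the person who coached the patient also prompts, reads out or records the answers, scores can shift in one arm only. No analysis can remove such a shift, because nothing in the data measures it.

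The closing sentence of section 3.3 makes this harder to see. Concealment protects the assignment and ends when the envelope is opened. A reader who takes that sentence at its word would credit the trial with protection during implementation that it does not have.

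**Working it through.** **1. The plan's own figure.** Inputs from section 3.1: alpha 0.05 (sidedness not stated; taken as two-sided), power 80%, standardised effect 0.78.

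- n per group = 2 × (1.960 + 0.842)² / 0.78² = 2 × 7.85 / 0.6084 = 25.8, so 26.
- With 20% attrition: 26 / (1 − 0.20) = 32.5, so 33.

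Both figures reproduce. They do not create the problem, but 26 evaluable per group is the base for step 3.

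**2. The passages side by side.**

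| Question | What the protocol gives |
|---|---|
| Who delivers? | The staff group in 4.2.2; the intervention team in 4.4.2 |
| Who follows up and collects data? | The same staff group in 4.2.2 |
| Who assesses symptoms regularly? | The intervention team in 4.4.2 |
| Who may complete the symptom form? | The patient, with unspecified questions open to medical personnel (9.1) |
| Who measures grip? | An exercise team whose other duties are not stated (section 6) |
| Who is blinded after allocation? | Nobody is named |

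Baseline assessment precedes assignment (section 3.2), so staff completion at baseline cannot depend on arm. The exposure is at follow-up. Follow-up use of the form is inferred from its date field; the time-point marks in Table 6 cannot be read in the text available.

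**3. Illustration of size.** The documents give no bias figure, so b (in SD units, favouring the intervention) is an assumption shown over a range. With no true effect and n per arm, the rejection probability of a two-sided 5% test is

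Φ(b√(n/2) − 1.96) + Φ(−b√(n/2) − 1.96).

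For n = 26, √(n/2) = 3.606. For n = 78 (3 × 26, if the three sites were pooled), √(n/2) = 6.245.

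| b (SD) | n = 26 per arm | n = 78 per arm |
|---|---|---|
| 0.1 | 0.065 | 0.096 |
| 0.2 | 0.111 | 0.239 |
| 0.3 | 0.191 | 0.466 |

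Example, b = 0.2 and n = 26: Φ(0.721 − 1.96) + Φ(−0.721 − 1.96) = 0.108 + 0.004 = 0.111 after rounding. For a fixed bias, more patients raise the error rate.

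**The case against.** The strongest reply is that the symptom items are written for self-completion. The hand, knee and hip sections and the M-SACRAH in section 9.3 all address the patient, and the only item that itself invites professional help is pathological type. The sentence about medical personnel probably had medical history in mind. This stands as far as intent goes, but the permission is general and does not exclude the symptom items.

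Section 4.2.2 also describes a category of staff with pooled duties, not three people who each do everything, and the nursing manager allocates tasks. That stands too. Separation is possible under the text, but it is not required.

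A reader might infer three stronger things that the documents do not support:

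- **That coaches fill in WOMAC for their patients.** Section 9.1 names neither those items nor the intervention staff.
- **That grip is measured by the people who deliver the intervention.** Whether the exercise team delivers anything is not stated. The test also follows a set procedure: three attempts with rests, highest value used.
- **That allocation concealment is deficient.** The envelope procedure is adequate as described; only its label and the protection claimed for it are wrong.

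Finally, the error rates rest on assumed biases. They do not separate staff influence from the reporting of patients who know their arm, and the pooled column assumes a test that section 3.1 does not set out.

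**Conclusion.** The point holds in a limited form. The text places delivery, follow-up data collection and symptom assessment in one team, leaves staff completion of the primary outcome's items open, and mislabels concealment as blinding. The mislabelling is a plain misstatement. The other two are gaps in safeguards: they permit provider influence on a subjective outcome without showing that it will occur.

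The size is unknown. About 6.5%, 11% and 19% at 26 per arm, or about 10%, 24% and 47% if three sites were pooled, are hypothetical error rates for assumed biases of 0.1, 0.2 and 0.3 SD. They should not be cited as the trial's error rate. The conclusion also rests on two inferences: that the form is used again at follow-up, and that no data collectors exist beyond those named. The change should be made before follow-up data are collected; the sample size is unaffected.

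**What to change.** 1. Reword the end of section 3.3 to say that the envelopes conceal allocation only, and that patients and providers are unblinded.
2. Require WOMAC and M-SACRAH to be self-completed at each follow-up assessment before contact with the nurse, and restrict staff completion to medical-history items. Use the same mode in both arms at a site. In Shanghai and Dali the app is the intervention vehicle, so app answers in one arm and paper in the other would add a new measurement difference.
3. Within the existing team, have help with reading items and the grip test done by someone other than the person who coaches that patient, unaware of allocation where feasible. State in section 4.2.2 or section 6 who the exercise team is and whether it delivers any of the programme.

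The cost is protocol wording and a small rota burden, felt most where only two staff are available. An assessor unaware of allocation cannot be promised in a team of two or three. Unblinded patients still report their own symptoms, so some bias remains and should be acknowledged when results are reported.

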4.3 Intervention and Follow-Up Duration (When)

This study includes a baseline survey, a 3-month intervention period, and a 3-month follow-up period, for a total duration of 6 months.

4.4 Intervention Location (Where)

4.4.1 Research Centers

- Shanghai, China: Comprehensive Treatment Outpatient Clinic, Fudan University Cancer Hospital
- Dali, China: Breast Oncology Outpatient Clinic, First Affiliated Hospital of Dali University
- Jakarta, Indonesia: Breast Oncology Department, Dharmais Cancer Hospital

4.4.2 Intervention Implementation Sites

(1) Medical Institutions

At each research center, the intervention team implements the following measures:

- **Patient Training:** Nurses provide personalized, face-to-face training to help patients understand musculoskeletal symptoms related to endocrine therapy and their management. Training content includes practical self-management skills, such as pain monitoring, medication side effect management, and guidance on diet and exercise.

- **Regular Assessment:** Nurses guide patients to attend regular hospital assessments of musculoskeletal symptoms during the intervention and follow-up periods. Standardized assessment tools are used to document symptom changes, and treatment plans are adjusted accordingly based on the results.

(2) Home-Based Self-Management

Patients follow the intervention plan for self-management in their daily lives, including the following components:

- **Self-Monitoring:** Regularly record musculoskeletal symptoms, such as pain intensity and stiffness.
- **Health Management:** Follow the intervention guidance provided by nurses for daily exercise, dietary adjustments, and medication management to ensure consistent intervention adherence and continuous monitoring and control of symptoms.
- **Data Feedback:** Patients regularly submit self-management records to the medical team for ongoing evaluation and adjustments.

4.5 Intervention Strategies

In this study, all research centers provide the same symptom management materials, but each center uses different media formats based on local resources and cultural context.

4.5.1 Shanghai and Dali, China

Patients manage their musculoskeletal symptoms through an app platform designed by the research team. The app offers symptom management materials across four main modules: Self-Monitoring and Reporting, Diet and Nutrition Management, Medication Adherence Management, and Exercise and Rehabilitation. Patients can record symptom changes, medication side effects, and daily diet and exercise plans on the platform. The nursing team provides personalized feedback and guidance through the platform, ensuring effective implementation of the intervention and continuous monitoring of patients' symptom management.

4.5.2 Jakarta, Indonesia

In Jakarta, the intervention is conducted offline. The nursing team provides patients

with the same symptom management content as the Chinese research centers, including Self-Monitoring and Reporting, Diet and Nutrition Management, Medication Adherence Management, and Exercise and Rehabilitation. Nurses distribute written and audio materials, offering detailed guidance for home-based self-management. Regular follow-ups and assessments are scheduled to ensure effective intervention implementation and positive outcomes.

5. Intervention Content (What)

Table 1: Evidence Extraction Table

Category	Evidence	Grade
Risk assessment	1. A thorough risk assessment of MS should be performed on the patient and inform relevant risk factors	3b
	2. Evaluation records should include age, BMI, hormone replacement therapy history, paclitaxel chemotherapy history, tamoxifen treatment history, cancer stage, date of last menstrual period, existing menopausal symptoms, or joint related diseases (e.g., osteoarthritis, rheumatoid arthritis)	3b
Symptom assessment	1. Commonly used assessment tools include the BPI-SF, M-SACRAH, PRAI, BCPT-MS, AUSCAN, WOMAC and ect.	1b
Preventions	1. Bone mineral density testing is performed before aromatase inhibitor treatment and once a year thereafter, and treatment with bisphosphonate or denosumab is considered based on the evaluation results	5b
	2. Instruct patients to take calcium and vitamin D supplements	5b
	3. For patients without MS, routine education should be done to strengthen patients' understanding of possible MS. Encourage the patient to participate in exercise and manage weight	5b
	4. Health education on the benefits and side effects of adjuvant endocrine therapy should be strengthened to improve compliance with endocrine therapy	5b
Interventions	1. Symptomatic treatment with acetaminophen or non-steroidal anti-inflammatory drugs	5b
	2. Traditional Chinese medicine could be a treatment option	1a

	3. Acupuncture is recommended to treat MS induced by aromatase inhibitors	1a
	4. Night splinting and nonsteroidal anti-inflammatory drugs could be used to relief carpal tunnel syndrome and stenosing tenosynovitis. If symptoms are refractory to nonsurgical intervention, surgical intervention may be warranted	3b
	5. Encourage moderate-intensity physical activity, 30 minutes a day, 5 times a week	1a
	6. A supervised exercise program, including aerobic exercise, resistance training, or a combination of both, is recommended, and the exercise intensity does not exceed 60% to 80% of the maximum heart rate, three times a week for 30 minutes each time	1a
	7. It is recommended to participate in yoga, Tai Chi, Health Qigong-Ba Duan Jin or other activities	2b
Monitoring	1. Increase the frequency of MS monitoring and follow-up every 3 to 6 months	5b

Table 2: Audit Criteria Extraction Table

Evidence	Audit criteria
1. A thorough risk assessment of MS should be performed on the patient and inform relevant risk factors	
2. Evaluation records should include age, BMI, hormone replacement therapy history, paclitaxel chemotherapy history, tamoxifen treatment history, cancer stage, date of last menstrual period, existing menopausal symptoms, or joint related diseases (e.g., osteoarthritis, rheumatoid arthritis)	1. The nurse assesses the patient's risk of MS, informs the relevant risk factors, and records them.
3. Commonly used assessment tools include the BPI-SF, M-SACRAH, PRAI, BCPT-MS, AUSCAN, WOMAC and ect.	2. The nurse uses a professional scale to assess the MS.
4. Bone mineral density testing is performed before aromatase inhibitor treatment and once a year thereafter, and treatment with bisphosphonate or denosumab is considered based on the evaluation results	3. The doctor tests the patient's bone mineral density once a year and gives treatment when appropriate.
5. Instruct patients to take calcium and vitamin D supplements	4. The nurse instructs the patient to take calcium and vitamin D supplements.

6. For patients without MS, routine education should be done to strengthen patients' understanding of possible MS. Encourage the patient to participate in exercise and manage weight

7. Health education on the benefits and side effects of adjuvant endocrine therapy should be strengthened to improve compliance with endocrine therapy

8. Symptomatic treatment with acetaminophen or non-steroidal anti-inflammatory drugs

9. Traditional Chinese medicine could be a treatment option

10. Acupuncture is recommended to treat MS induced by aromatase inhibitors

11. Night splinting and nonsteroidal anti-inflammatory drugs could be used to relief carpal tunnel syndrome and stenosing tenosynovitis. If symptoms are refractory to nonsurgical intervention, surgical intervention may be warranted

12. Encourage moderate-intensity physical activity, 30 minutes a day, 5 times a week

13. A supervised exercise program, including aerobic exercise, resistance training, or a combination of both, is recommended, and the exercise intensity does not exceed 60% to 80% of the maximum heart rate, three times a week for 30 minutes each time

14. It is recommended to participate in yoga, Tai Chi, Health Qigong-Ba Duan Jin or other activities

15. Increase the frequency of MS monitoring and follow-up every 3 to 6 months

5. The nurse delivers the patient health education about MS.

6. The doctor prescribes acetaminophen or non-steroidal anti-inflammatory drugs, traditional Chinese medicine, acupuncture, night splinting other treatments when appropriate.

7. The nurse instructs the patient to participate in exercise.

8. The nurse regularly monitors patients for MS.

5. Intervention Content (What)

